13.2 Clinical Laboratory

For continuous hematology, chemistry, and urinalysis tests, observed values, changes from primary baseline, and percent changes from primary baseline will be summarized descriptively by visit and treatment group as defined in Section 5. Categorical urinalysis tests will be summarized using frequencies by visit and treatment group. Of note, hematology, chemistry, and urinalysis tests will only be collected in subjects ≥ 12 years of age at time of enrollment in the parent study.

Shift tables from primary baseline to each post-baseline visit describing shifts to out-of-normal range will be provided for chemistry, hematology, quantitative and qualitative urinalysis tests. Only subjects with a baseline result and a result at the specified post-baseline visit for the test will be considered.

Listings of abnormal laboratory will be provided for each test where a subject had at least one abnormal result.

Laboratory data will be presented in SI units.

13.3 Vital Signs

For each vital sign (systolic blood pressure, diastolic blood pressure, heart rate, body temperature, weight, and height for subjects <18 years), observed values, changes from primary baseline and percent changes from primary baseline will be summarized descriptively by visit and treatment group as defined in Section 5.

The number and percentage of subjects with a gain or lose $>5\%$ in body weight from primary baseline to each OLE post-baseline visit will be summarized by visit and treatment group as defined in Section 5. A similar summary further broken down by age group (refer to Section 6.6) will also be provided.

For adults (≥ 18 years), the BMI observed values will be summarized using descriptive statistics by treatment group as defined in Section 5. For children (2 to 11 years) and adolescents (12 to 17 years), the BMI percentile rather than BMI observed value will be summarized using descriptive statistics by treatment group as defined in Section 5.

A listing of all vital sign assessments, including weight and BMI, will be provided.

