6.9. Clinical Laboratory Results and Vital Signs

All clinical laboratory results (subjects ≥ 12 years old) and vital signs measurements will be summarized descriptively by parameter, visit, and treatment group along with time point of collection.

A shift from baseline table describing out-of-normal range shifts will be provided for clinical laboratory results.

A shift from baseline table will identify subjects who gain or lose $>5\%$ body weight over the course of the study.

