- SCORAD Total Score = [Overall BSA affected by AD / 5] + [Intensity score * 7/ 2] + Subjective symptoms score (i.e., pruritus + sleep loss), ranging from 0 to 103. SCORAD total score will be set to missing if information for any of the three measures is missing.
- Change from baseline = Assessment value at post-baseline visit X – baseline value.
- Percent change from baseline = (Assessment value at post-baseline visit X – baseline value) × 100% / (baseline value)

Percent change from baseline will be missing in situation where baseline value equals to 0.

- Exposure-adjusted incidence rate (EAIR) = (number of subjects with an event / total within-arm exposure [days]) * 365.25 days/year * 100.
- BMI (kg/m²) = (weight in kg)/ [(height in cm/100)²]. For child and adolescent (2 to 17 years), after BMI is calculated, it is expressed as a percentile using data files and instructions provided by the CDC (https://www.cdc.gov/growthcharts/percentile_data_files.htm).

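### The 5% weight-change table uses one cut-off for all ages, so a child who fails to gain is not counted, and no planned summary gives growth-referenced change from baseline in subjects under 18

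*SAP*

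**What the plan says.** **Categorical rule.** SAP 13.3 reports "The number and percentage of subjects with a gain or lose $>5\%$ in body weight from primary baseline to each OLE post-baseline visit", by visit and treatment group. It adds "A similar summary further broken down by age group", using the Section 6.6 groups (2–5, 6–11, 12–17 and 18 years or older). The cut-off is the same in each group. Protocol 6.9 has the same rule: "A shift from baseline table will identify subjects who gain or lose" more than 5% of body weight, with no adjustment for age.

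**Continuous summaries.** For vital signs, including weight and (under 18) height, SAP 13.3 states that "changes from primary baseline and percent changes from primary baseline will be summarized descriptively by visit and treatment group". The treatment groups are those of SAP Section 5. No age split is attached to this summary.

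**Growth-referenced measure.** SAP 5.5 derives BMI for ages 2 to 17, and "it is expressed as a percentile using data files and instructions provided by the CDC". SAP 13.3 then says "the BMI percentile rather than BMI observed value will be summarized using descriptive statistics by treatment group". No change from baseline, shift or threshold is stated for it. SAP Section 8 lists baseline BMI in kg/m² by age band and does not mention the percentile.

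**Listing and alerts.** All weights and BMI values are listed. The two protocol instructions to report weight to the medical monitor (Section 1.3, footnote c, and Section 5.1.5) both concern loss.

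**The concern.** Children are expected to gain weight over a follow-up of 24 or 52 weeks. A fixed percentage change from baseline reads differently in them than in adults: zero change is neutral in an adult but a shortfall in a growing child, and the table treats the two alike. Splitting the table by age does not help while the cut-off stays the same.

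Weight matters here because protocol 2.3.2 lists weight loss among the most common adverse events of oral roflumilast, and protocol 2.4.2 says the known oral effects can be monitored as this protocol specifies. The extension has a single arm and no untreated children, so an age and sex reference is the available way to separate growth from a treatment effect. Subjects aged 2 to 11 also have no routine safety laboratory tests and no PK sample, which leaves weight as one of their few objective systemic measures.

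**Working it through.** **Who is affected.** The protocol's Summary of Changes raises enrolment from about 400 to about 1500. It names about 275 + 275 = 550 added subjects aged 6–17, which is 550/1500 = 37%. It also adds all ARQ-151-315 roll-overs (ages 2–5) without giving a number; by subtraction this is 1500 − 400 − 550 = 550. If all the added places go to children, the paediatric share is at least (1500 − 400)/1500 = 73%. Only the 37% is stated outright.

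**What the 5% table misses.** The plan has no figure to reproduce. The documents give no growth rate, so annual growth g is an assumption, shown from 3% to 15%.

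- Expected growth over w weeks: G = (1 + g)^(w/52) − 1.
- A child with no gain has a 0% change and enters neither category. The shortfall against expected weight is G/(1 + G).
- To be counted as a loss of more than 5%, the shortfall must exceed 1 − 0.95/(1 + G).

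Example, g = 10% at 52 weeks: 0.10/1.10 = 9.1%, and 1 − 0.95/1.10 = 13.6%.

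| Annual g | 24 wk: expected gain | 24 wk: unflagged shortfall, no gain | 24 wk: shortfall to be counted as loss | 52 wk: unflagged shortfall, no gain | 52 wk: shortfall to be counted as loss |
|---|---|---|---|---|---|
| 3% | 1.4% | 1.4% | 6.3% | 2.9% | 7.8% |
| 5% | 2.3% | 2.2% | 7.1% | 4.8% | 9.5% |
| 8% | 3.6% | 3.5% | 8.3% | 7.4% | 12.0% |
| 10% | 4.5% | 4.3% | 9.1% | 9.1% | 13.6% |
| 12% | 5.4% | 5.1% | 9.8% | 10.7% | 15.2% |
| 15% | 6.7% | 6.2% | 10.9% | 13.0% | 17.4% |

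For an adult with G = 0 the threshold is simply 5%. The roughly 550 added subjects aged 6–17 form Cohort-Week 24, so the 24-week columns apply to them. For subjects who had roflumilast in the parent study, primary baseline lies about four weeks earlier, which makes the figures slightly larger.

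**The gain category.** Once expected growth exceeds 5%, a normally growing child is counted as a gain of more than 5%. At 52 weeks this happens for g above 5%; at 24 weeks it happens somewhere between g = 10% and 12%.

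**What the other summaries can show.**

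- *Weight and height change.* For ARQ-151-311/312 roll-overs the Section 5 groups pool ages 6 to adult, so a mean change mixes growing children with adults. Cohort-Week 24 leaves after Week 24, so the mix also changes between Week 24 and Week 36. For ARQ-151-315 roll-overs the groups contain only young children, so pooling with adults does not arise, but there is still no growth reference.
- *BMI percentile.* With no weight gain and assumed annual height growth h, BMI falls by 1 − 1/(1 + h)² at 52 weeks: 5.7% for h = 3% and 12.7% for h = 7%. At 24 weeks the fall is 2.7% to 6.1%. The measure would therefore respond. As planned it is a summary of levels, and without within-child change a fall in a minority of children can be lost in the group average.

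**The case against.** The strongest reply is that weight safety does not rest on the 5% table. SAP 13.3 also plans weight and height change by visit, a CDC-referenced BMI percentile, and a full listing. Mean weight change near zero beside rising height would point to failure to gain, and the BMI calculation confirms that the percentile would move. This stands, and it limits the point: a reader might infer that failure to gain would be invisible, and the documents do not support that.

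A reader might also infer that BMI percentile is not summarised by visit, because SAP 13.3 does not say so in that sentence. SAP 5.6 says that summary tables are presented by visit where applicable. Height under 18 is measured at every clinic visit, and vital signs have analysis windows in SAP Table 3. By-visit display is probably intended, and only the explicit statement is missing.

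It is also fair to say that the growth rates are unsourced, that the 52-week figures are too large for the 24-week cohort, and that the study is descriptive with no hypothesis tests, so no planned result becomes wrong. Weight-related adverse events are reported separately as TEAEs, by age group for ARQ-151-311/312 roll-overs.

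Three things remain after this. No subject-level category captures failure to gain, no growth-referenced change from baseline is stated, and the continuous weight and height changes are not split by age. A listing of up to about 1500 subjects does not replace a summary.

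**Conclusion.** The point holds as a gap in the planned displays. One cut-off serves all ages, a child with no gain is not counted, and the remaining summaries show such a child only indirectly. Under assumed annual growth of 3% to 15%, the uncounted shortfall is about 3% to 13% of expected weight at 52 weeks and about 1% to 6% at 24 weeks. At the low end over 24 weeks this is small.

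The result depends on the assumed growth rates; the ARQ-151-315 share of enrolment is inferred by subtraction. That a weight effect in children would appear as failure to gain is a plausible inference that the documents do not state, and it is weaker for adolescents near final height.

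A reader might go on to conclude that the 5% table should be kept for adults only. The documents do not support that: protocol 6.9 specifies the table without an age limit, and dropping it in children would lose the count of frank weight loss. The change is worth making because it is cheap, the data are already collected, and without a control arm it is the direct way to separate growth from a weight effect.

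**What to change.** Keep the 5% table for all ages. For subjects under 18, add to SAP 13.3 the change from primary baseline in CDC BMI percentile or z-score, summarised by visit (stated explicitly), by treatment group and by the Section 6.6 age groups. Add baseline BMI percentile to the baseline table in SAP Section 8. A count of subjects with a downward shift may be included if the sponsor fixes the size of the shift in advance.

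The cost is one derived variable and one table. Weight and height are already recorded at every clinic visit for subjects under 18, and the CDC files are already cited in SAP 5.5, so no new data collection is needed.

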I agree to maintain the confidentiality of all information received or developed in connection with this protocol.

Investigational Site Name: _____

Print Investigator Name: _____

Investigator Signature: _____ Date: _____

SUMMARY OF CHANGES

The following sections have been changed in Amendment 1 of the ARQ-151-313 protocol:

Version/Date	Description
December 20, 2020	Original Protocol
Amendment 1 September 17, 2021	
Added Summary of Changes section.Added statement that during the conduct of the study, additional countries and/or sites may be added if necessary.Sample size increased from approximately 400 to approximately 1500 subjects to allow:
All subjects from ARQ-151-315 to enroll into the ARQ-151-313 Open Label Extension study.An additional ~275 subjects ages 6-17 from ARQ-151-311 and additional ~275 subjects ages 6-17 from ARQ-151-312 to enroll into the ARQ-151-313 Open Label Extension study for a 24-week treatment period. This is Cohort-Week 24.Clarification added that if an unscheduled visit is required for reasons other than safety, the following assessments are not required:
vIGA-AD and EASIBSA affected with ADLocal tolerability assessment (by Investigator)Removed all safety labs for subjects ages 2-11; safety labs would have been evaluated at screening in the preceding study and the investigator may order safety labs at any time during the study to evaluate an adverse event.WI-NRS:
Added statement that caregiver/parents will be given instructions on how to complete this questionnaire for subjects between 2 and 5 years of age.Added that parent and/or guardian will be trained at the baseline visit to assist the subject, if needed, in the accurate completion of the WI-NRS for subjects \geq 6 years of age.Added clarification that only subjects 18 years and older will be enrolled at sites located in the province of Québec in Canada.

Version/Date	Description

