4.3. Subject Participation

Subject participation involves a minimum of five clinic visits at Week 4, Week 12, Week 24, Week 36 and Week 52 of treatment. There will be three phone visits conducted at Weeks 18, 30 and 44. (For Cohort-Week 24, subject participation involves a minimum of three clinic visits at Week 4, Week 12 and Week 24 of treatment. There will be one phone visit conducted at Week 18). The Day 1 visit of this study will be Week 4 of the ARQ-151-311 or ARQ-151-312 or ARQ-151-315 study. The baseline value for safety and efficacy will be the last observation prior to the first dose of ARQ-151 cream in either the ARQ-151 preceding study (ARQ-151-311 or ARQ-151-312 or ARQ-151-315), or this study. The anticipated maximum duration of subject participation is about 24 or 52 weeks. Subjects in the ARQ-151-311 or ARQ-151-312 or ARQ-151-315 study that choose to participate in the long-term extension study will transition directly into the ARQ-151-313 study at the Day 1 visit (Week 4 of Study ARQ-151-311 or ARQ-151-312 or ARQ-151-315).

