5.5. Early Termination Visit

If a subject is withdrawn or wishes to exit the study, a termination visit will be scheduled. This visit should include the procedures and assessments that would be performed at the Week 52 visit.

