5.4 Windowing Conventions

The scheduled visit will be used to report measurements for summaries by visit regardless of whether this visit was performed within or outside of the analysis visit windows. Unscheduled visit, early termination (ET) visit, and/or retest measurements will only be used for the summaries by visit if a scheduled measurement is not available and the unscheduled/retest/ET measurement

 Innovaderm Research	STATISTICAL ANALYSIS PLAN, Final Version 1.0
Protocol Number: ARQ-151-313	Sponsor: Arcutis Biotherapeutics, Inc.

falls within the analysis visit windows described in [Table 3](#), [Table 4](#), [Table 5](#), and [Table 6](#). Scheduled, unscheduled, ET, and retest measurements will be listed.

If there is more than one assessment for a given analysis visit when a scheduled measurement is not available, the assessment closest to the target day will be considered. If two assessments are equidistant to the target day, the latest assessment will be used.

Table 3 OLE Analysis Visit Windows – vIGA-AD, EASI, BSA Affected by AD, DLQI, CDLQI, IDQOL, DFI, SCORAD, POEM, Vital Signs, Local Tolerability Assessments, PHQ-8, PHQ-A, CDI-2, and C-SSRS

Analysis Visit	Target Day	Window (Days)
OLE Week 4	29	15 to 57
OLE Week 12	85	58 to 127
OLE Week 24	169	128 to 211
OLE Week 36	253	212 to 309
OLE Week 52	365	≥ 310

Table 4 OLE Analysis Visit Windows – WI-NRS

Analysis Visit	Target Day	Window (Days)
OLE Week 1	8	5 to 11
OLE Week 2	15	12 to 18
OLE Week 3	22	19 to 25
OLE Week 4	29	26 to 32
OLE Week x	y	z1 to z2
OLE Week 52	365	≥ 362

where: x= 5 to 51; y= (x * 7) + 1; z1 = y – 3, and z2 = y + 3.

Table 5 OLE Analysis Visit Windows – Clinical Laboratory

Analysis Visit	Target Day	Window (Days)
OLE Week 24	169	15 to 267
OLE Week 52	365	≥ 268

 Innovaderm Research	STATISTICAL ANALYSIS PLAN, Final Version 1.0
Protocol Number: ARQ-151-313	Sponsor: Arcutis Biotherapeutics, Inc.

Table 6 OLE Analysis Visit Windows – Physical Examination

Analysis Visit	Target Day	Window (Days)
OLE Week 4	29	15 to 127
OLE Week 24	169	128 to 267
OLE Week 52	365	≥ 268

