5.8 Handling of Retests, Unscheduled Visits, and Early Termination Data

Retests measurements, unscheduled measurements, and ET visit assessments will be included in analysis and be summarized via analysis visit windowing according to the windowing conventions in section 5.4.

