16 APPENDICES

Appendix 1

Output Conventions

TLF will be generated using SAS® and will be displayed on letter size paper with landscape orientation, 1-inch margins and 9 pt. Courier New font.

The header section will comprise the sponsor's name, the protocol number, the delivery description, the data cut-off date (if applicable), the TLF number, the TLF title, the analysis set, and the page number (Page X of Y). The footer section will include the TLF footnotes, the CRO's name, the date and time of the execution of the program, and the name of the program.

The mean, median, geometric mean will be displayed to one more decimal place than the original value; Q1, Q3, minimum and maximum will keep the same number of decimal places as the original value; standard deviation, standard error, CV and CI will be displayed to two more decimal places than the original value. If derived parameters are to be summarized, the number of decimals of the derived values is to be chosen on a case-by-case basis, but the rule above applies.

For categorical summary tables, percentages will be reported to one decimal place. Percentages between 0 and 0.1 (both exclusive) will be displayed as “<0.1”. The denominator for each percentage will be the number of subjects within the population per treatment group unless otherwise specified.

Listings will be ordered by treatment received in parent study and this study, subject number, date and visit (where applicable). Imputed dates will not be presented in the listings.

Dates & Times Format

Date and time (if available) will be presented in the format yyyy-mm-dd/hh:mm.

 Innovaderm Research	STATISTICAL ANALYSIS PLAN, Final Version 1.0
Protocol Number: ARQ-151-313	Sponsor: Arcutis Biotherapeutics, Inc.

Presentation of Treatment Groups

When applicable, study treatments will be represented as follows in the different outputs:

For summary tables:

Parent Study Treatment Full Name	Study Treatment Output Name	Notes:
Roflumilast cream 0.15%	Roflumilast cream 0.15%	ARQ-151-311/312 roll-overs
Vehicle	Vehicle / Roflumilast cream 0.15%	ARQ-151-311/312 roll-overs
n/a	Pooled Roflumilast cream 0.15%	ARQ-151-311/312 roll-overs
Roflumilast cream 0.05%	Roflumilast Cream 0.05% or 0.15%	ARQ-151-315 roll-overs
Vehicle	Vehicle / Roflumilast cream 0.05% or 0.15%	ARQ-151-315 roll-overs
n/a	Pooled Roflumilast cream 0.05% or 0.15%	ARQ-151-315 roll-overs

For listings and figures:

Parent Study Treatment Full Name	Study Treatment Output Name	Notes:

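### SAP 13.3 counts weight change above 5% only by visit, so no SAP table gives the proportion of subjects who ever lost more than 5%, and some early-termination weights reach only the listing

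*SAP*

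**What the plan says.** SAP 13.3 (Vital Signs) tabulates subjects whose weight rises or falls by more than 5%. The change "in body weight from primary baseline to each OLE post-baseline visit will be summarized by visit and treatment group". A second version adds a split by age group. All vital signs, weight included, are also listed.

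SAP 5.4 (Windowing Conventions) governs which weights reach a by-visit table. Unscheduled, ET and retest "measurements will only be used for the summaries by visit if a scheduled measurement is not available", and then only if they fall inside the analysis window. SAP 5.8 offers no other route: "ET visit assessments will be included in analysis and be summarized via analysis visit windowing according to the windowing conventions in section 5.4".

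ET visits do produce a weight. Protocol 5.5 says of the ET visit: "This visit should include the procedures and assessments that would be performed at the Week 52 visit". The schedule in Protocol 1.3 includes weight at Week 52/ET.

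Protocol 6.9 describes a shift table that identifies subjects with weight gain or loss above 5%, framed over the whole study rather than visit by visit.

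**The concern.** Protocol 2.3.2 names weight loss among the most common adverse events of oral roflumilast and mentions clinically significant loss in two prospective studies. Protocol 2.4.2 says the topical profile appears different. A reader of a long-term safety study will therefore ask what share of subjects lost more than 5% at some point.

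By-visit rows do not answer that. They do not show whether the subjects above the threshold at Week 12 are the same ones as at Week 24. In addition, the weights that can miss the tables include the last weights of people leaving the study, and some of them may be leaving because of weight loss.

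**Working it through.** The plan states no figure on this point, so there is none to reproduce.

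**1. Which weights are left out.** Inputs: SAP Table 3 windows and target days.

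| Visit | Target day | Window | Days after target, same window |
|---|---|---|---|
| Week 4 | 29 | 15-57 | 57 - 29 = 28 |
| Week 12 | 85 | 58-127 | 127 - 85 = 42 |
| Week 24 | 169 | 128-211 | 211 - 169 = 42 |
| Week 36 | 253 | 212-309 | 309 - 253 = 56 |
| Week 52 | 365 | 310 onward | not applicable |

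Take a subject weighed at Week 12 on Day 85 who leaves with an ET weight on Day 100. Both days lie in the 58-127 window. The scheduled weight takes the Week 12 slot, and the next window does not open until Day 128, so the Day 100 weight enters no by-visit table. If the subject first passed 5% loss between those two days, the by-visit weight tables do not show it. An ET weight on Days 2-14 (13 days) lies in no window.

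If visits fall on their target days:

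- 52 weeks: possible ET days are Days 2-364 less four visit days, 363 - 4 = 359. Left out: 13 + 28 + 42 + 42 + 56 = 181, or 181/359 = 50%.
- Cohort-Week 24: Days 2-168 less two visit days, 167 - 2 = 165. Left out: 13 + 28 + 42 = 83, or 83/165 = 50%.

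These are shares of calendar days. They show that the rule is not confined to a rare corner of the schedule. They do not say how many subjects are affected, because the documents do not say when withdrawals will occur.

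**2. What by-visit rows can say about any-time loss.** Let p_v be the proportion with loss above 5% at visit v, on a common denominator. For weights that enter the table:

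largest p_v ≤ p_any ≤ min(1, sum of p_v)

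The documents give no weight-loss rate, so equal assumed rates are used as illustration:

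| Assumed p_v at every visit | Three visits (Cohort-Week 24) | Five visits (Cohort-Week 52) |
|---|---|---|
| 2% | 2% to 6% | 2% to 10% |
| 5% | 5% to 15% | 5% to 25% |
| 10% | 10% to 30% | 10% to 50% |

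The upper ends require that no subject passes the threshold at more than one visit. That is unlikely for repeated weights on one person, so the truth would tend to lie below them. ET weights left out under step 1 fall outside this bound and could add to p_any. Even if every ET weight were admitted, by-visit rows would still not give p_any, so the windowing rule is the secondary cause.

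**3. Denominator.** For laboratory shifts, SAP 13.2 says: "Only subjects with a baseline result and a result at the specified post-baseline visit for the test will be considered". SAP 13.3 has no such sentence. The Appendix 1 default is: "The denominator for each percentage will be the number of subjects within the population per treatment group unless otherwise specified". Amendment 1 planned about 275 subjects aged 6-17 from ARQ-151-311 and an "additional ~275 subjects ages 6-17 from ARQ-151-312", so about 275 + 275 = 550 in Cohort-Week 24. For them, "subject participation involves a minimum of three clinic visits at Week 4, Week 12 and Week 24 of treatment", so they have no weight at Weeks 36 and 52. Under the default they would still be in the denominator there. The documents do not give the expected number of other 311/312 rollovers, so the dilution cannot be sized.

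**The case against.** The strongest reply is that by-visit tabulation is a legitimate descriptive choice and that the clinical risk is covered elsewhere. Every weight is listed. A loss of 5% or more goes to the medical monitor (Protocol 1.3, weight footnote). Weight loss recorded as an adverse event enters the TEAE tables, and if it leads to discontinuation it is tabulated there too. Outside Days 2-14, a left-out ET weight belongs to a subject who already has a scheduled weight in that window, so what is lost is a later reading and not the subject. All of this stands, and it limits the weight of the point. But a listing for up to about 1500 subjects is not a summary, and neither the monitor reports nor the TEAE tables count subjects by measured loss.

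Three stronger readings are tempting, and the documents do not support them.

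- *That the SAP contradicts Protocol 6.9 through a change not declared in SAP 3.6.* The protocol wording is compatible with an any-time count but can also mean net change, and SAP 13.2 likewise carries out the parallel laboratory sentence by visit.
- *That half of ET weights are lost.* The 50% is a share of days; the timing of withdrawals is unknown.
- *That Week 36 and Week 52 percentages will be diluted.* The default yields to any other specification, and the table layouts are in a separate document. The issue is also not specific to weight, and the age-group split already keeps the adult and 2-5 year strata free of Cohort-Week 24.

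**Conclusion.** The point holds as a cheap and useful improvement. No table described in the SAP gives the proportion of subjects who ever lost more than 5%, and a withdrawing subject's last weight may be visible only in the listing. This rests on the text of SAP 5.4, 5.8 and 13.3 and assumes that the separate table shells add no any-time row.

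The number of subjects affected cannot be estimated from the documents. The bounds above depend on assumed rates and show only how little the by-visit rows pin down. The denominator is a matter for clarification, because the shells may already settle it.

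**What to change.** In SAP 13.3:

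- Add one row with the number and percentage of subjects with loss above 5% from Primary baseline at any OLE post-baseline weight, including ET and unscheduled weights. Count each subject once. The denominator is subjects with a baseline and at least one post-baseline weight. Show it by treatment group and age group.
- Show gain above 5% in its own row, read mainly in adults because children grow.
- Keep the by-visit table and state that its denominator is subjects weighed at that visit, in line with SAP 13.2.

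The cost is about two sentences and a few table rows, from weights already collected. The downside is in interpretation: any-time figures are higher than by-visit ones, rise with the number of weighings, include transient fluctuation and have no concurrent control. The retained by-visit table gives context. Because Cohort-Week 24 has three weighings and Cohort-Week 52 has five, a footnote on cohort is useful. A full split by cohort should stay optional, since SAP 3.6 dropped general by-cohort analyses.
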